5.1 Selection of Study Population

5.1.1 Inclusion Criteria

In order to be eligible to participate in this study, an individual must meet all of the following criteria:

1. Be 18+ years of age and older
2. Own or have regular access to a smartphone with a recent operating system installed (Android: OS 8.0 or higher, Apple: iOS 13.0 or higher) with reliable Wi-Fi access or sufficient data plan to engage with assigned treatment condition for the duration of the study
3. Available and committed to engage with the program and complete assessments for a 2-week duration
4. Able to read and write in English
5. Participants must have primary residence in the United States

5.1.2 Exclusion Criteria

An individual who meets any of the following criteria will be excluded from participation in this study:

1. Current suicidal ideation with a plan and/or intent or a suicide attempt within the past 12 months
2. Previous Woebot use

5.2 Screen Failures

Participants who sign study consent and do not meet inclusion/exclusion criteria at Screening, will be considered a Screen Failure. Participants will be notified that they did not meet eligibility criteria and provided with a set of resources. Re-screens will not be permitted in this study. De-identified participant ID numbers assigned to participants who screen fail will not be reused.

5.3 Withdrawal of Participants from the Study

If a participant decides to withdraw consent from the study, they will be removed from future study activities and any data collected before withdrawal may be retained and used in study analyses. In addition, a participant may be withdrawn by the investigator if the participant violates the study plan, or for administrative and/or other safety reasons.

Discontinuation of study treatment for a participant occurs when study treatment is stopped earlier than the protocol planned duration and can be initiated by either the participant or the investigator. The investigator must discontinue study treatment for a given participant if he/she believes that continuation would negatively impact the participant's well-being. Involvement in the study is strictly voluntary. Participants have the right to withdraw from the study at any time for any reason, without any reprisal.

Participants should be discontinued from the study if any of the following occur:

1. It is discovered that the participant shared app images/screenshots publicly
2. The participant withdraws consent to participate in the study
3. The participant develops an illness that would interfere with their continued participation in the study
4. The participant has an SAE rated as Grade 3 (severe) or higher (see Section 8.3.2)
5. The participant is noncompliant with treatment schedule, study procedures, in the opinion of the investigator and per the protocol, where applicable
6. The PI, Sponsor, IRB, or regulatory agency requests withdrawal of the participant
7. Any other reason relating to the participant's safety or integrity of the study data as determined by the Safety Assessment Committee (SAC)

Participants who withdraw or are withdrawn from the study may be replaced. Participants who withdraw or are withdrawn from the study cannot subsequently rejoin the study.

If a participant withdraws or is withdrawn from the study for reasons related to safety, the study Sponsor-Investigator and SAC will be informed immediately.

If the participant withdraws consent for disclosure of further information, the Sponsor-Investigator may retain and continue to use any collected data before such a withdrawal of consent.

Although a participant is not obliged to give a reason for withdrawing from a study, the investigator should make a reasonable effort to ascertain the reason, while fully respecting the participant's rights.

6. Study Assessments and Procedures

All assessments, and their corresponding administration points, are listed in Table 1.

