11. Ethics and Responsibilities	33
11.1 Good Clinical Practice	33
11.2 Institutional Review Board	33
11.3 Informed Consent	34
12. Records Management	35
12.1 Source Documentation	35
12.2 Case Report Form Completion and Data Management	35
12.3 Study Files and Record Retention	36
13. Auditing and Monitoring	36
13.1 Protocol Adherence and Deviations	37
14. Amendments	37
15. Study Start and Termination	38
16. Confidentiality	38
17. References	38

Schedule of Events

Visit Weeks/Days	Screening Period	Treatment Period	
	Screening / Baseline Day -6 to Day 1	Week 1 Day 3 (+2)	Week 2 (EOS/ET) Day 14 (+6)
Informed Consent	X		
Eligibility Confirmation (Inclusion/Exclusion)	X		
Demographics	X		
Psychiatric History	X		
Prior & Concomitant Medications/Therapy	X		X
[REDACTED]	[REDACTED]		
[REDACTED]	[REDACTED]		[REDACTED]
[REDACTED]	[REDACTED]		[REDACTED]
Participant Identity Verification ^a	X		
Randomization	X		
Register within the Study Application	X		
CSQ-8 ^b			X
[REDACTED]		[REDACTED]	[REDACTED]
[REDACTED]		[REDACTED]	[REDACTED]
[REDACTED]		[REDACTED]	[REDACTED]
[REDACTED]			[REDACTED]
Assessment of AE/SAEs			X
App Engagement Metrics (collected throughout study)			X
Termination of App Access			X

^a Video call with designated study team member ^b Self-Report Clinical Assessment
EOS = End of Study
CSQ-8 = Client Satisfaction Questionnaire; [REDACTED]

Participants will have up to one week from the time of providing informed consent to complete all screening and baseline tasks including registering for the study application. Participants will not be withdrawn for failing to register for the app. Date of randomization will be considered Day 1.

1. Introduction

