3.3.2 Randomization

Randomization into the treatment arms will be 1:1 with no additional stratification by group demographics. The study may over enroll in order to meet 75 completed participants in each treatment arm. Participants will be considered randomized once they complete all of their screening and baseline activities including surveys, their identity has been verified, and eligibility has been confirmed (e.g., checked for duplicate registrations).

[figure not shown]
[figure not shown]

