4.3 Trial Intervention Compliance

Trial intervention compliance will not be monitored in this study and participants will not be removed from the study for failing to register and/or not regularly engaging with their assigned treatment. Instead, intervention compliance will be assessed post study during analysis. Compliance may be defined as opening the app at least once per week for a minimum of 50% of weeks (1 of 2) during the intervention period.

5. Study Population

Participants will be recruited through the Lindus Health CitrusRecruit network which utilizes a combination of participant sources including but not limited to existing patient databases, primary care networks, and targeted social media campaigns. Those interested in participating will be invited to complete a survey to confirm they meet the pre-screening criteria (excluding questions about suicidal ideation and attempt) and be presented with the opportunity to independently review and electronically sign the study consent form. Upon signing the consent form, participants will be asked to schedule a video call during which a designated member of the virtual site team will verify the participants identity. After successful completion of the verification call, participants will be provided with a secure link to complete the screening/baseline survey. Participants will be asked questions about their current suicidal ideation with plan and/or intent as well as an attempt in the past 12 months. People who do not meet study criteria based on suicidal ideation/attempt will be notified that they may benefit from a level of care beyond the scope of the study and that if they feel they are in need of immediate medical care they should contact 911 or go to their nearest emergency room and reach out to someone they trust that can help them stay safe. Additional resources will also be provided electronically. If a participant endorses

presence of current suicidal plan and/or intent, the study PI will attempt to follow-up with the participant (up to three times). See Section 8.5.1 of this protocol for more details.

Approximately ~165 adults will be randomized for this study to ensure a final sample of 150 completers (e.g., randomized and completed all study activities through Week 2; assuming a 10% attrition rate).

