7.1 Early Study Termination

The study can be terminated by the Sponsor-Investigator at any time. Reasons for early termination include:

- Study recruitment or retention is too low for the study to provide meaningful results
- Unanticipated, significant, or unacceptable safety risk to participants enrolled in the study
- Decision based on recommendations from Sponsor-Investigator and SAC after review of safety and efficacy data

- Discontinuation of study if Sponsor-Investigator, in collaboration with study team members and SAC, determine from planned analyses that the app is not efficacious or if there are safety concerns.

In making the decision to terminate, the Sponsor-Investigator and SAC will always consider the participants' welfare and safety. Should early termination be necessary, participants must be contacted as soon as possible to conduct EOS assessments, if willing, and treated as a prematurely withdrawn participant. Additional procedures may be provided to ensure that adequate consideration is given to the protection of the participant's interests. The Sponsor-Investigator will be responsible for informing Institutional Review Boards (IRB) of the early termination of the trial.

8. Data and Safety Monitoring

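### Does the noncompliance withdrawal rule in Section 5.3 put the single CSQ-8 measurement at risk?

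*Combined protocol and SAP*

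**What the plan says.** Section 5.3 opens its list with "Participants should be discontinued from the study if any of the following occur", and item 5 reads "The participant is noncompliant with treatment schedule, study procedures, in the opinion of the investigator and per the protocol, where applicable". The same section adds that "Participants who withdraw or are withdrawn from the study may be replaced". It covers keeping data gathered before withdrawal and asking for the reason, but the readable text does not mention obtaining the CSQ-8 from someone who is discontinued.

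Section 4.3 says that compliance is not tracked while the study runs and is looked at only in the analysis, and that "participants will not be removed from the study for failing to register and/or not regularly engaging with their assigned treatment". The note under the Schedule of Events is narrower: "Participants will not be withdrawn for failing to register for the app".

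The Schedule marks the CSQ-8 once, in the column whose heading begins "Week 2 (EOS/ET) Day 14 (+6". Section 3.1 has surveys going to all participants at baseline, Day 3 and Week 2, and allows reminders. Section 7.1, on closure of the whole study, says "participants must be contacted as soon as possible to conduct EOS assessments, if willing, and treated as a prematurely withdrawn participant". Section 3.3.2 says "The study may over enroll in order to meet 75 completed participants in each treatment arm".

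Section 9.2 defines the intent-to-treat sample as those randomised who have survey data, without naming the survey. Section 10.6 reports missing counts in every descriptive table and rules out imputation. Section 9.3 describes the study as internal, exploratory and descriptive, with no power calculation.

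**The concern.** Read alone, item 5 lets an investigator remove someone from the study for not following the treatment schedule, while 4.3 says that low engagement is not a ground for removal. If staff acted on item 5, the people removed would be the less engaged, who may also be the less satisfied. The CSQ-8 is taken once and nothing is imputed, so a score not obtained is lost to the primary summary. Section 5.3 does not ask for it, and the one explicit request for end-of-study assessments from early leavers, in 7.1, concerns termination of the whole study. Replacement and over-enrolment seem to add to the worry, because a completer could take the place of the person removed. At stake would be an overstated satisfaction score in one or both arms, and a distorted contrast if removals differed by arm.

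**Working it through.** **The plan's own figure.** The protocol plans about 165 randomised for 150 completers at 10% attrition. 150 × 1.10 = 165, and 150 / 0.90 = 167; either agrees with about 165. Planned loss from all causes is 165 − 150 = 15, or 7.5 per arm. Removal for noncompliance would be an unstated part of that.

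**Is there a trigger?**
- Item 5 is limited by its closing words, which refer back to the protocol. The specific provision on intervention compliance is 4.3, and item 5 can be read as yielding to it.
- 4.3 sets up no monitoring during the study, and the readable text gives no app-use schedule to breach. Low engagement is therefore not something staff are set up to act on before Week 2.
- The other limb of item 5, study procedures, is not addressed by 4.3, so there is no conflict there.
- The Schedule note overlaps with item 5 only on failure to register.

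**Would the CSQ-8 still be sought?** The Week 2 column is shared with an ET label, 3.1 sends the Week 2 survey to all participants, and 7.1 links end-of-study assessments with being handled as a premature withdrawal. Together these point to collection at early exit, although 5.3 does not say so. Those who withdraw consent leave all further activities and are outside this question.

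**Would a loss be visible?** Under 3.3.2 a person counts as randomised only after completing the baseline surveys. If any survey suffices in 9.2, everyone randomised is in the intent-to-treat sample, and 10.6 then shows how many lack the CSQ-8. Reading the survey in 9.2 as the CSQ-8 itself would make that count zero by construction, so the broader reading is the natural one.

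**Size.** Suppose k people in an arm are lost and score g points below those observed. If n is the number who would otherwise have been scored, the observed arm mean is too high by k × g / n. The documents give neither k nor g. Taking g from 3 to 8 and 75 completers plus k lost:

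| k | g = 3 | g = 8 |
|---|---|---|
| 1 | 3/76 = 0.04 | 8/76 = 0.11 |
| 2 | 6/77 = 0.08 | 16/77 = 0.21 |
| 3 | 9/78 = 0.12 | 24/78 = 0.31 |

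The scale runs from 8 to 32, so one lost score can move an arm mean by at most 24/76 = 0.32.

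**Does replacement make it worse?** Without replacement, k lost from 75 gives k × g / 75; with replacement the divisor is 75 + k. For k = 3 and g = 8 that is 24/75 = 0.32 against 24/78 = 0.31. Adding completers does not raise the expected observed mean, and it slightly reduces the error.

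**For scale.** With an assumed SD of 4, 5 or 6 and 75 per arm, the 95% half-width for the arm difference, 1.96 × SD × √(2/75), is 1.28, 1.60 or 1.92 points. If all three losses at g = 8 fell in one arm and none in the other, the contrast would shift by 0.31, about a quarter of the smallest half-width (0.31/1.28 = 0.24). The plan itself computes no such interval.

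**The case for a change.** The best case for acting is that the gap does not depend on noncompliance. Section 5.3 has other routes out that do not involve withdrawing consent, such as sharing screenshots, illness, a severe SAE, or a request from the sponsor or IRB, and it asks for the CSQ-8 in none of them. ET is not expanded in the readable text, 7.1 is about closing the study, and a score not requested at Week 2 cannot be recovered at analysis. If item 5 does yield to 4.3, its treatment-schedule limb has little left to do. A sentence or two would cost almost nothing.

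Part of this stands. Section 5.3 lacks a pointer to the EOS/ET column, and item 5 is loosely worded beside 4.3. But the abbreviation line under the Schedule is partly redacted, as is the contents entry directly after 4.3, so the missing definition may not be the plan's own omission. A blanket request to everyone discontinued would also reach people removed for illness or safety, without the willingness condition in 7.1; that goes well beyond the noncompliance wording. Finally, nothing shows that the extra scores would alter a descriptive summary. The investigator whose opinion item 5 invokes is meant to be blinded unless a safety event intervenes, which limits any difference between arms.

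**Conclusion.** No change to the statistical plan follows. The wording of 5.3 item 5, 4.3 and the Schedule note is in tension and must be reconciled by the sponsor; that is an editorial matter, and this note takes no view on which withdrawal rule should govern. The missing pointer from 5.3 to the EOS/ET column, and the unnamed survey in 9.2, are gaps that the study team and analysts would fill sensibly from 3.1, 3.3.2, 10.6 and the Schedule.

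The likely effect on an arm mean is unknown and probably very small: 0.04 to 0.31 points for 1 to 3 removals per arm with gaps of 3 to 8 points, all assumed. The arm contrast moves only if removals or gaps differ by arm. With no hypothesis test, margin or decision rule attached to the CSQ-8, no planned conclusion turns on a shift of that size. The judgement assumes that 4.3 is followed as written and that Week 2 surveys go out as 3.1 describes. It concerns the readable text only.

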6.1 Screening/Baseline Assessments and Procedures

6.1.1 Demographic Questions

In an effort to ensure equitable access and representation as well as assess clinical efficacy in diverse populations, Woebot Health has researched current best practices and language around demographic data collection, and developed a health equity demographic battery. The demographic battery consists of age, biological sex, gender identity, sexual orientation, race, ethnicity, education, marital status, employment status, living situation, able bodiedness, physical health conditions, and health insurance status.

6.1.2 Psychiatric History

Participants will be asked to complete questions about their history of diagnosed mental health disorders.

6.1.3 Concomitant Medication and Therapy

Participants will be asked to complete questions evaluating whether they are currently seeing a mental health professional (i.e., therapist, social worker), whether they are currently taking any psychotropic medications, as well as satisfaction with concurrent mental health treatment.

6.1.5 Eligibility Verification Call

[figure not shown]
After signing the study eICF, participants will be asked to schedule an eligibility verification video call with a member of the decentralized study team. During this call the designated member of the study team will ask the participant to verify their identity (e.g., show a government issued ID), confirm their contact information and DOB.

6.2 Efficacy Assessments and Procedures

6.2.1 Satisfaction

The Client Satisfaction Questionnaire (CSQ-8)

The CSQ-8 is an 8-item measure used to assess client's satisfaction with treatment on a 4-point scale (1 = "very dissatisfied" to 4 = "very satisfied"). Example questions include, "how would you rate the quality of service you received?" and "did you get the kind of service you wanted?" Total sums range from 8-32, with high scores indicating greater satisfaction with Woebot. The CSQ-8 has been widely disseminated and considered both valid and reliable (α ranges = .83-.93).²

[REDACTED]

[REDACTED]

Safety Assessments

Safety events will be captured through participant spontaneous report, in-app content, and via a self-report assessment of Adverse Events (AE) collected at the Week 2/EOS visit. See Section 8.5 for further detail.

7. Study Stopping Rules

Study procedures will be stopped if the Sponsor-Investigator, in discussion with the SAC and/or IRB as applicable, determines that the number and/or severity of AEs justify putting the study on hold.

The study may resume following the safety review, if the Sponsor-Investigator agrees it is safe to proceed.

The Sponsor-Investigator may initiate study closure at any time, provided there is reasonable cause and sufficient notice is given in advance of the intended termination.

7.1 Early Study Termination

The study can be terminated by the Sponsor-Investigator at any time. Reasons for early termination include:

- Study recruitment or retention is too low for the study to provide meaningful results
- Unanticipated, significant, or unacceptable safety risk to participants enrolled in the study
- Decision based on recommendations from Sponsor-Investigator and SAC after review of safety and efficacy data

- Discontinuation of study if Sponsor-Investigator, in collaboration with study team members and SAC, determine from planned analyses that the app is not efficacious or if there are safety concerns.

In making the decision to terminate, the Sponsor-Investigator and SAC will always consider the participants' welfare and safety. Should early termination be necessary, participants must be contacted as soon as possible to conduct EOS assessments, if willing, and treated as a prematurely withdrawn participant. Additional procedures may be provided to ensure that adequate consideration is given to the protection of the participant's interests. The Sponsor-Investigator will be responsible for informing Institutional Review Boards (IRB) of the early termination of the trial.

8. Data and Safety Monitoring

8.1 Risk and Benefit Assessment

8.1.1 Risks

Given that the research aims to enroll participants into a low-risk intervention, we do not anticipate that participation in the study will be associated with elevated risk. [REDACTED]

[REDACTED] The overall evaluation of risk is that it is low.

8.1.2 Procedures for minimizing risk

Misunderstanding the Capabilities of the Application

The 'Build' app is not intended to be a crisis service, however there is the potential that participants may misunderstand the limitations of the app. To mitigate this risk, the study will provide clear information on the capabilities of the app, intended use, and limitations of the app at consent, randomization, and key points throughout. Resources are also accessible within the app as well as will be sent to the participant in the event that they are requested.

Data Breach

All study data are gathered on either a HIPAA-compliant web platform that resides behind Woebot Health security firewalls or via HIPAA-compliant online platforms, thus actual risk from data breach for study data is low. Research material obtained from human subjects will include self-report questionnaires and conversations and engagement data within the 'Build' app. All data obtained via Woebot will be encrypted and stored on Amazon Web Services (AWS) and/or Google Cloud Platform; Woebot Health data gathering and storage procedures are compliant with both HIPAA and the European Union's General Data Protection Regulation. Only members of the research team will have access to identifiable study data. De-identified data will be accessible to the product development team (designers, user researchers, and product managers) as well as the research team.

Potential Upset due to Study Procedures

Foreseeable risks to participants include the possibility that some assessment questions and/or treatment procedures may be upsetting to participants. Experience with similar populations has indicated that the risk of emotional upset during the assessments is low and if it occurred, the upset would likely be temporary and not be serious in nature. Such risks will be minimized by the thoughtful

selection of questionnaires. Participants will also be informed that they may withdraw from the study at any time and if requested, appropriate resources will be provided.

There is also a potential risk for upset upon discontinued access to the study intervention at end of treatment/study (Week 2). Participants are informed during the consent process and are reminded at onboarding of how long they will have access to the intervention for. Return to care and other resources are provided upon removing access to the 'Build' app.

Participants can refuse and withdraw from participation at any time. If they withdraw consent from the study, they will no longer have access to the study treatments.

